### **7.2.6 Follow-up**

Eligible patients will be followed from their cohort entry until the occurrence of the outcome of interest, death, the last date of follow-up available in the data set, or the study end date.

Patients will be censored in the respective cohort if they:

- Had stopped their treatment with sacubitril/valsartan or ACEI
- Added treatment with another renin-angiotensin-aldosterone system (RAAS blocking agent (i.e., add-on of an ACEI [only for initiators of sacubitril/valsartan], an ARB, or aliskiren)

- Switched initial treatment to another RAAS blocking agent (i.e., sacubitril/valsartan to an ACEI, ARB or aliskiren; ACEI to sacubitril/valsartan, an ARB, or aliskiren [switching within the ACEI class, however, was not censored])
- Stopped contributing data to the database (e.g., patient died, or left the practice/health insurance, etc.), whichever will occur first.

See [Section 7.3.1](#) for detailed definitions regarding discontinuation, add-on, or switching.

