## 5.2 Hypotension

In the double-blind period of the PARADIGM-HF trial, hypotension and clinically relevant low systolic blood pressure (<90 mmHg and decrease from baseline of >20 mmHg) were reported in 17.6% and 4.8% of sacubitril/valsartan treated patients compared to 11.9% and 2.7% of enalapril treated patients, respectively, with hypotension reported as a serious adverse event (AE) in approximately 1.5% of patients in both treatment arms. Hypotension was more commonly reported for patients >65 years old, and those with renal disease. A recent systematic review and meta-analysis of RCTs identified a significantly increased risk of hypotension of sacubitril/valsartan versus active control treatment (risk ratio: 1.45 [95% CI: 1.27-1.67] based on 13 RCTs) and a risk increase of similar magnitude when compared to ACEIs (risk ratio: 1.49 [95% CI: 1.15-1.95] based on five RCTs) (Martins et al 2021).

Hypotension is included in the Entresto® RMP as an identified risk.

Hypotension is often observed in HF patients for whom multiple HF therapies are used, as most of these therapies (i.e., ACEIs/ARBs,  $\beta$ -blockers, mineralocorticoid receptor antagonists [MRAs], diuretics) have blood pressure-lowering effects (Yancy et al 2013). Sacubitril/valsartan also has a blood pressure lowering effect based on its ARB and neprilysin inhibitor properties. Patients with an activated renin-angiotensin system, such as volume- and/or salt-depleted patients (e.g. those being treated with high doses of diuretics), are at greater risk for hypotension.

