### **Exclusion criteria**

- Use of sacubitril/valsartan by patients with prior angioedema history is contraindicated; patients with a recorded angioedema diagnosis prior to index date (see [Section 7.2.5](#) for definition of ‘index date’) are excluded from all cohorts.
- Patients with concurrent prescriptions or pharmacy fills for sacubitril/valsartan and ACEI (i.e., prescription/pharmacy fill on the same day) will also be excluded and will be reported to reflect violation of the 36-hour washout period of ACEI prior to initiation of sacubitril/valsartan.
- For the assessment of ‘hepatotoxicity’, we will exclude patients with a hepatotoxic event prior to index date (chronic, acute, viral [including HIV], alcohol- or drug-induced, or codes without defined cause [e.g., “hepatitis unspecified”]. Patients with codes indicating hepatic morbidity suggestive of another etiology [“other specified disorders of liver”, biliary or alcohol-induced hepatotoxicity]) before or up to 7 days after the index date will be excluded. This will account for late determination or recording thereof of the excluded etiology of the event.
- Patients with a recorded history of chronic renal disease will be excluded for the assessment of ‘renal impairment’.

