### **7.2.5 Cohort start**

The date of the first recorded prescription (or pharmacy fill) for sacubitril/valsartan or ACEI in the study period will be defined as the cohort entry (= start of follow-up or ‘index date’). A minimal look-back period of 365 days is used to determine baseline characteristics.

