### 7.3.2 Safety events of interest

The safety events of interest include a recorded diagnosis of:

- Angioedema (primary event of interest; as ‘*narrow*’ [primary analysis] and ‘*hypersensitivity reaction*’ [sensitivity analysis])
- Hypotension (as ‘*narrow*’ [primary analysis] and ‘*broad*’ [sensitivity analysis])
- Hyperkalemia
- Hepatotoxicity
- Renal impairment

as identified from in- and/or outpatient registry or claims data, or electronic medical records. Recorded abnormal laboratory values (for identification of hyperkalemia) will also be included for identification of outcomes of interest, if available (not available for ARS and GePaRD).

Safety events of interest will be identified using the event-specific codes based on the coding system(s) used in the databases of interest (e.g. READ, ICD-9/-10 CM, ICD-10 GM, or ICPC codes (see [Table 7-8](#) for details). A detailed knowledge of the healthcare systems in the different countries is necessary to provide the correct definitions for all safety events.

An initial list of terms that would be used for the event definition mapping is supplied in Annex [Section 12.3](#). Additional natural language processing (NLP) terms will be used in PHARMO to further differentiate within ICPC codes.

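### Hypotension and hyperkalaemia have no event-free rule before index and no index-day rule, so persisting or same-day records count as incident events

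*Protocol*

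**What the plan says.** Protocol section 7.2.4 sets endpoint-specific rules on prior history:

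- **Angioedema:** "patients with a recorded angioedema diagnosis prior to index date" are removed from all cohorts.
- **Hepatotoxicity:** "we will exclude patients with a hepatotoxic event prior to index date". Codes pointing to another etiology are also excluded up to 7 days after index, to allow for late recording.
- **Renal impairment:** "Patients with a recorded history of chronic renal disease will be excluded for the assessment of" this endpoint. The rule covers chronic disease and does not mention prior acute kidney injury.
- **Hypotension and hyperkalaemia:** no rule.

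Section 7.2.5 says that the date of the first recorded prescription or fill "will be defined as the cohort entry (= start of follow-up or ‘index date". It gives the look-back one purpose: "A minimal look-back period of 365 days is used to determine baseline characteristics". Section 7.2.6 then states: "Eligible patients will be followed from their cohort entry until the occurrence of the outcome of interest". Neither section says how a record on the index day is treated.

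On ascertainment, section 7.3.2 states: "Recorded abnormal laboratory values (for identification of hyperkalemia) will also be included for identification of outcomes of interest", except in ARS and GePaRD, where they are not available. Table 12-1 lists orthostatic hypotension, dizziness and syncope among the hypotension terms. Neither condition appears among the baseline comorbidities in section 7.3.3.

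**The concern.** The primary and secondary objectives are incidence rates after starting treatment, and both conditions can be present before it. Section 5.2 says "Hypotension is often observed in HF patients for whom multiple HF therapies are used". Section 5.3 links hyperkalaemia to ACEIs, ARBs and MRAs. Section 7.1.1 expects most sacubitril/valsartan starters to have used an ACEI or ARB before.

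Two kinds of record can therefore enter the numerator without being new events:

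- A patient whose potassium was already above the cut-off before the switch, and still is at the first check afterwards.
- A patient with orthostatic hypotension coded, or blood drawn, on the day of the first recorded prescription.

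Each adds an event with almost no person-time. The inflation would fall mainly in the first weeks, and the interim reports give rates by week of use (section 7.7.1.1). Because neither condition is tabulated at baseline, a reader could not judge from the planned tables how much of the rate was carried over.

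**Working it through.** **The plan's own figure.** The Abstract and section 7.5 give 132 angioedema cases in 24,000 PY. 132/24,000 = 5.50 per 1,000 PY, with an exact Poisson 95% CI of 4.60 to 6.52. This agrees with the stated 5.5 (4.6 to 6.5). Angioedema has a prior-event exclusion, so the figure neither supports nor weakens the point. The protocol gives no study-size figure for hypotension or hyperkalaemia.

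**Inputs.** 29,000 starters and 24,000 PY (Abstract), so 24,000/29,000 = 0.828 PY per starter. In the feasibility set, GePaRD supplied 4,724 of 5,185 starters (section 7.1.2). The share *f* of starters with a carried-over or index-day record is not in the documents and is an assumption throughout.

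**Coded records, all databases.** Added rate = *f* × 29,000 / 24,000 PY.

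| Assumed *f* | Added events | Added rate per 1,000 PY |
|---|---|---|
| 0.1% | 29 | 1.2 |
| 0.5% | 145 | 6.0 |
| 1% | 290 | 12.1 |
| 2% | 580 | 24.2 |
| 5% | 1,450 | 60.4 |

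The relative effect depends on the true rate, which is also unknown. Suppose *f* = 1% and the affected patients add no person-time. The denominator is then 24,000 × 0.99 = 23,760 PY, and 290/23,760 adds 12.2 per 1,000 PY. Assumed true rates of 20, 50 and 100 per 1,000 PY become 32.2, 62.2 and 112.2.

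**Early follow-up.** If all records for *f* = 1% fell in the first week, the week-1 rate would rise by 0.01/(7/365.25) = 0.522 per PY, or about 522 per 1,000 PY.

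**Laboratory potassium.** This route is absent in ARS and GePaRD. Taking out GePaRD alone at its feasibility share:

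- GePaRD share: 4,724/5,185 = 91.1%, leaving 8.9%.
- Other starters: 0.0889 × 29,000 ≈ 2,578, of whom 1% is about 26.
- Crude pooled effect: 26/24,000 ≈ 1.1 per 1,000 PY. Taking out ARS lowers it further.
- Effect within those databases, at the same mean exposure: 26/(0.0889 × 24,000) = 26/2,134 ≈ 12 per 1,000 PY.

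The crude pooled laboratory effect is therefore small, but the database-specific rates, which are also reported, are not protected.

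**The case against.** The strongest reply is that the statistical analysis plan may settle this. Sections 7.3.2.2 and 7.3.2.3 leave code lists, and for hypotension the algorithms, to that document, which was not available here. Section 7.7.1.2.3 leaves the event-misclassification sensitivity analyses to it. That is fair for code lists. It is less convincing for who is at risk, because section 7.2.4 fixes that for three of the five events and sections 7.2.5 and 7.2.6 fix the start of the clock.

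A second reply is that the three existing rules are not a uniform precedent. The angioedema exclusion follows from a contraindication, and the renal rule removes chronic disease rather than the acute outcome. This stands: only the hepatotoxicity rule, in part, is a close model. It also stands that both conditions can recur, so a lifetime exclusion would remove patients at higher risk and change the target population.

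A reader might infer more than the documents support:

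- **That the rates will be 12 to 60 per 1,000 PY too high.** No share is given. The frequencies in sections 5.2 and 5.3 are on-treatment trial figures, not prevalence before index. Only findings recorded again on or after index count, blood pressure readings are not used, and some of these patients would later have had a genuine event.
- **That index-day records precede intake.** Sections 7.1.2 and 7.9 say that the true start may be missed, so some may be on-drug events.
- **That the contrast between cohorts is distorted.** This is plausible but not shown. Cohorts 2 and 4 are free of ACEIs and ARBs for 365 days, but MRA use is allowed.

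**Conclusion.** The gap is real and lies in the eligibility and follow-up rules of the protocol itself. It biases the hypotension and hyperkalaemia rates upward in all four cohorts, mainly early in follow-up. Both are secondary events. Angioedema has its own exclusion, and the hazard ratios in section 7.7.1.2.2 cover angioedema only, so neither is affected.

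The size cannot be derived from the documents. The results above are conversions for an assumed share. They rest on the planned total exposure and, for the laboratory route, on the feasibility share of GePaRD holding in the final data. The added rate is *f* divided by mean exposure per starter. The primary analysis is censored at 31 December 2019, so its mean exposure may differ from 0.83 PY and the conversion would change with it.

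The potassium criterion is itself unsettled: section 7.3.2.3 defines hyperkalaemia as above 5 mmol/L, while Table 12-1 uses above 5.4 and prints the unit as nmol/l. The lower threshold would bring in more baseline values.

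**What to change.** For hypotension and hyperkalaemia, add to sections 7.2.4 to 7.2.6:

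1. Require no record of the same event (code or, where available, potassium above the cut-off) in a short fixed window up to and including the index day, for example 30 days. Alternatively, start the clock for such patients after an event-free interval. Do not use a lifetime exclusion.
2. Count events from the day after index.
3. Report the rate without these rules as a sensitivity analysis, because some index-day records may be on-drug events after a missed initiation.
4. Reconcile the potassium cut-off and unit between section 7.3.2.3 and Table 12-1, since the window depends on them.

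The cost is one condition per endpoint in the common script and no new data. The downside is that some recently affected patients leave the main risk set for that endpoint, and genuine same-day events appear only in the sensitivity analysis.

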## 7.3 Variables

### 7.3.1 Exposures of interest

Exposures of primary interest are sacubitril/valsartan, ACEIs, and ARBs.

Exposure information will be identified using prescription or pharmacy fill data using the database specific coding system (e.g., Anatomical Therapeutic Chemical [ATC] Classification; British National Formulary [BNF]/Gemscript coding). Any use of ACEIs/ARBs will be included. The duration of each prescription/dispensing will be calculated by dividing the amount by the prescribed dose (if available) and otherwise by the national defined daily dose (DDD) equivalent by the World Health Organization (WHO). Episodes of treatment will be created for sacubitril/valsartan and for ACEIs/ARBs for all prescriptions in the same group if there are less than 90 days between the end of the previous prescription and the start of the new one. Overlap in prescriptions of the same kind will be disregarded (no ‘stockpiling’).

We will consider patients as ACEI- or ARB-naïve if they do not use an ACEI or ARB recorded within 365 days before the index date, respectively.

We will consider patients as having discontinued treatment if there is a gap in a series of successive prescriptions or pharmacy fills of the index drug class that is  $\geq 90$  days after the estimated treatment end of the last prescription or pharmacy fill preceding the gap. The calculated end of the prescription/dispensing will be defined as the date of discontinuation, at which point patients’ follow-up time will be censored. In the case where the follow-up ends before the 90 days are over a patient will not be considered to have discontinued.

Four exposure groups (cohorts) will be defined: two for sacubitril/valsartan-, and two for ACEI-users.

#### 7.3.1.1 Sacubitril/valsartan user cohorts

- Sacubitril/valsartan initiators regardless of prior ACEI/ARB use (cohort 1)

This group includes all patients fulfilling the inclusion criteria ([Section 7.2.4](#)) and using sacubitril/valsartan during the study period – regardless of prior exposure to ACEIs or ARBs.

- Sacubitril/valsartan initiators treatment naïve to ACEIs/ARBs (cohort 2)

Cohort 2 is the subset of patients from cohort 1- who did not use ACEIs/ARBs in the 365 days prior to the index date.

---

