### 6.1 Primary objective

1. To estimate the incidence of specific safety events of interest in HF patients newly starting treatment with sacubitril/valsartan (regardless of prior use of ACEIs or ARBs)

The primary safety event of interest is:

- Angioedema

Secondary events of interest are:

- Hypotension
- Hyperkalemia
- Hepatotoxicity
- Renal impairment

2. To estimate the incidence of all specific safety events (as mentioned above) in HF patients newly starting treatment with sacubitril/valsartan without prior exposure to ACEIs or ARBs

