As the risk of ACEI-associated angioedema is highest very shortly after treatment initiation and decreases over time ([Kostis et al 2005](#), [Miller et al 2008](#), [Toh et al 2012](#)), a cohort of prevalent ACEI users would be biased towards a lower angioedema risk compared to ACEI naïve patients. The majority of patients experiencing angioedema while treated with ACEIs can be expected to discontinue ACEI treatment and would therefore unlikely be part of a prevalent ACEI user cohort. Thus, comparing sacubitril/valsartan initiators regardless of their prior exposure to ACEIs/ARBs, to ACEI initiators who are treatment naïve to ACEIs and ARBs is likely to bias the comparative (explorative) analysis in favor of sacubitril/valsartan. Therefore, it is considered that the optimal comparison is between sacubitril/valsartan initiators who are treatment naïve to ACEIs/ARBs and ACEI initiators without prior ACEIs/ARB use. To provide an estimate of what may happen if prevalent users are included, we will explore all these analyses (see [Section 6.3](#) Exploratory objectives).

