Accruing the required sample size for the comparison of patients initiating sacubitril/valsartan treatment without prior ACEI/ARB use with those newly initiating treatment with ACEIs/ARBs within the proposed timelines will be very unlikely. It should be expected that many HF patients (both prevalent and incident) will have been previously exposed to an ACEI used as treatment for hypertension or other comorbid diseases prevalent in HF patients (e.g., acute myocardial infarction, diabetic nephropathy). A US study in patients with incident HF diagnosed between 2005 and 2008 from four sites participating in the Cardiovascular Research Network (CVRN) found an exposure prevalence to ACEIs or ARBs in patients with incident HFrEF (n=3,941, mean age 69 years) of 43% ([Goldberg et al 2013](#)). In the European ‘ESC-HF Long-Term Registry’ a prospective cohort study with primary data collection, including over 7,400 patients with prevalent chronic HF (median age 66 years) were enrolled over two years. In the subgroup of patients with HFrEF (n=4,792), 92.2% were treated with ACEIs or ARBs at baseline ([Maggioni et al 2013](#)). Thus, indicating that the absolute number of ACEI initiators who are treatment naïve to ACEIs and ARBs will be limited. If necessary, it was initially planned to supplement the contemporaneous comparator cohort with a historical cohort of ACEI initiators who are treatment naïve to ACEIs using data prior to Entresto® market approval if needed. However, the most recent interim report for the LCZ696B2014 study identified a total of 116,041 ACEI initiators being treatment naïve to ACEIs/ARBs [REDACTED] when both ARS and GePaRD were included. Based on these results, inclusion of a historical cohort of ACEI initiators treatment naïve to ACEIs/ARBs does not seem necessary.

In addition, to explore the impact of depletion of susceptibles we will assess the rate of events in users of ACEIs with prior use of ACEIs/ARBs.

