### 7.3.1.2 ACEI user cohorts

- ACEIs – users regardless of prior ACEI/ARB use (cohort 3)

[figure not shown]
This group includes all patients fulfilling the inclusion criteria ([Section 7.2.4](#)) and using ACEIs during the study period – regardless of prior exposure to ACEIs or ARBs. This cohort will be a mix of prevalent and incident ACEI users.

- ACEIs – without prior use of ACEI/ARB - treatment-naïve (cohort 4)

Cohort 4 is the subset of patients from cohort 3. It includes patients who did not use ACEIs/ARBs in the 365 days prior to index date. This sub-cohort corresponds to new ACEIs users - naïve to ACEIs/ARBs.

Note: Patients can be included in more than one cohort. Patients changing from ACEI to sacubitril/valsartan will be included in the corresponding ACEI cohort, as well as the sacubitril/valsartan cohort (only the first change will be considered). Patients changing from sacubitril/valsartan to an ACEI, however, will be censored. [Figure 7-2](#) illustrates cohort allocation and start of follow-up based on various exposure scenarios for sacubitril/valsartan and ACEI users.

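### Cohorts 2 and 4 share a written 365-day naïve rule, but first-fill indexing imposes a longer ACEI-free period on cohort 4, so the comparison called optimal is unequal in prior ACEI use

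*Protocol*

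**What the plan says.** Primary objective 2 (Section 6.1) concerns patients "newly starting treatment with sacubitril/valsartan without prior exposure to ACEIs or ARBs", and exploratory objective 1 compares such patients with ACEI initiators who are likewise without prior exposure. The Abstract and Section 7.3.1 make naïve operational as no ACEI or ARB in the 365 days before index.

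- Cohort 2 (Section 7.3.1.1): "Cohort 2 is the subset of patients from cohort 1- who did not use ACEIs/ARBs in the 365 days prior to the index date".
- Cohort 4 (Section 7.3.1.2): "Cohort 4 is the subset of patients from cohort 3". Its naïve rule reads: "It includes patients who did not use ACEIs/ARBs in the 365 days prior to index date".
- Index date (Section 7.2.5): "The date of the first recorded prescription (or pharmacy fill) for sacubitril/valsartan or ACEI in the study period will be defined as the cohort entry". The legend to Figure 7-2 makes this cohort-specific: first sacubitril/valsartan fill for cohorts 1 and 2, first ACEI use for cohorts 3 and 4.
- Study period (Section 7.2.3): it opens at the launch date in each country.
- Multiple membership (note in Section 7.3.1.2): a patient who moves from an ACEI to sacubitril/valsartan is counted in both the ACEI and the sacubitril/valsartan cohort.

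Section 7.1.1 holds that prior ACEI/ARB users have a lower baseline angioedema risk because susceptible patients have already been removed. It concludes that "the optimal comparison is between sacubitril/valsartan initiators who are treatment naïve to ACEIs/ARBs and ACEI initiators without prior ACEIs/ARB use".

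**The concern.** The two naïve cohorts are worded alike but do not screen alike, because the index date works differently in each. In cohort 4 the index is itself the first ACEI fill since launch, so an earlier post-launch fill is impossible. In cohort 2 the index is a fill of the other drug, and only the preceding year is checked for ACEI use.

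Consider a patient who takes an ACEI in 2016, stops in 2017 and starts sacubitril/valsartan in 2019. That patient enters cohort 2 as naïve although the study holds the ACEI record, and may already have contributed to cohort 4. The mirror-image patient, who stops an ACEI in 2017 and restarts one in 2019, cannot enter cohort 4 at the restart, because the 2016 fill fixed the index.

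What is at stake is the hazard ratio for exploratory objective 1. The protocol prefers this contrast because depletion of susceptibles distorts the comparison of cohort 1 with cohort 4. If cohort 2 holds more people who have already tolerated an ACEI than cohort 4 does, part of that distortion returns.

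**Working it through.** **Inputs.** Launch dates and study durations come from Table 7-1. The end of the main analysis period, 31 December 2019, comes from Section 7.7.1.2.2. The index and naïve rules are those set out above. The protocol gives no figure for the share of former ACEI users in cohort 2.

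**Check of the plan's own figures.** Counting months inclusively from launch to the end of data reproduces every duration in Table 7-1: Aarhus 61, GePaRD 48, HSD 57, ARS 61, PHARMO 54, SIDIAP 57, CPRD 61.

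**Required ACEI-free period at t months after launch.**
- Cohort 2: 12 months, whatever t is.
- Cohort 4: max(12, t) months.

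The two agree for t ≤ 12 and differ by t − 12 months afterwards.

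**Size of the difference up to 31 December 2019.** Let L be the months from launch to that date. If index dates are spread evenly over L (an assumption), the share with t > 12 is (L − 12)/L, and the mean cohort 4 requirement is [12 × 12 + (L² − 12²)/2]/L. For GePaRD, L = 48: (48 − 12)/48 = 0.75, and (144 + 1,080)/48 = 25.5 months.

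| Database | L, also the longest cohort 4 requirement (months) | Share of index dates with t > 12 | Mean cohort 4 requirement (months) | Cohort 2 requirement (months) |
|---|---|---|---|---|
| Aarhus, CPRD | 49 | 0.76 | 26.0 | 12 |
| GePaRD | 48 | 0.75 | 25.5 | 12 |
| HSD, ARS | 45 | 0.73 | 24.1 | 12 |
| PHARMO | 42 | 0.71 | 22.7 | 12 |
| SIDIAP | 39 | 0.69 | 21.3 | 12 |

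These figures measure how unequal the entry rules are. They do not measure bias.

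**What the inequality could do to the hazard ratio (illustration only).** Let f be the share of cohort 2 follow-up from former post-launch ACEI users, and r their angioedema risk relative to the rest of cohort 2. The hazard ratio is then multiplied by approximately 1 − f(1 − r):
- f = 0.10, r = 0.75: 1 − 0.10 × 0.25 = 0.975
- f = 0.20, r = 0.5: 1 − 0.20 × 0.5 = 0.90
- f = 0.50, r = 0.25: 1 − 0.50 × 0.75 = 0.625
- r = 1: 1.0 for any f
- r above 1: a multiplier above 1

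Neither f nor r can be taken from the protocol.

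**Can the planned adjustment absorb it?** Section 7.3.3 assesses prior ACEI and ARB use over the 365 days before index, excluding the index date. Within cohorts 2 and 4 both covariates are zero by definition, so the propensity score of Section 7.7.1.2.2 contains no information on earlier use. The exclusion of recorded prior angioedema (Section 7.2.4) applies to all cohorts, but it leaves former users who tolerated an ACEI in cohort 2.

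**The case against.** The strongest reply is that the written rule is identical in both cohorts and openly disclosed, and that the asymmetry is a narrow by-product of indexing. Much of this stands.

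- **Scope.** For ARBs both cohorts have only the 365-day check, and in the first year after launch the ACEI requirements coincide. Cohort 4 may also contain ACEI users from before launch whose use ended more than 365 days before index. A reader might infer that cohort 4 is a never-user group; it is not.
- **Primary objective 2.** A reader might infer that this objective goes unanswered because former users are admitted. The protocol defines naïve as 365 days, and the objective is a single-arm rate, so an inequality between arms does not touch it.
- **Direction.** Former users stopped their ACEI. Section 7.1.1 expects most patients with ACEI angioedema to discontinue, and the exclusion catches only recorded angioedema. Unrecorded reactors among former users would raise the cohort 2 rate.
- **Frequency.** It is tempting to read the registry figure in Section 7.1.1 ("92.2% were treated with ACEIs or ARBs at baseline") as showing that most of cohort 2 are former users. It describes current treatment in prevalent HFrEF. The same section gives 43% in incident HFrEF, and neither figure gives former use among patients with none in the last year.
- **Status.** Section 6.3 declares all comparisons exploratory because of potential selection biases, and Section 7.9 expects major issues with the naïve cohorts. The protocol does not claim this comparison is free of bias.

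Two points are not answered. The caveats in Sections 6.3 and 7.9 are general and do not name this asymmetry, and no planned analysis would reveal it. Section 7.2.5 alone might be read as one shared index date for either drug, but the Figure 7-2 legend and the note on multiple membership exclude that. The drawing in Figure 7-2 was not available here, so any restart scenario it shows should be checked.

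**Conclusion.** The point holds in limited form. For ACEIs, and for index dates more than 365 days after launch, exploratory objective 1 compares cohorts with different ACEI-free requirements: 12 months against the time since launch, which reaches 39 to 49 months by the end of 2019. If index dates are spread evenly, 69% to 76% of them fall where the requirements differ, and the mean requirement in cohort 4 is about 21 to 26 months.

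The protocol's depletion argument makes a bias in favour of sacubitril/valsartan the expected result, but does not demonstrate it. The sign depends on whether former users in cohort 2 are mainly tolerators, and the size on how many there are; the protocol gives neither. The conclusion rests on the cohort-specific reading of the index date. It does not extend to the single-arm incidence rates, nor does it show the 365-day washout to be unsuitable in itself.

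**What to change.** For exploratory objective 1, add an analysis of cohort 2 versus cohort 4 under one symmetric rule. Either of these would serve:

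1. Also exclude from cohort 2 any patient with an ACEI fill between launch and the sacubitril/valsartan index date. This gives cohort 2 the condition that cohort 4 already meets.
2. Require, in both cohorts, no recorded ACEI or ARB in all extracted history, with a minimum of 365 days. This also covers ARBs and pre-launch use, but look-back length then varies with database and entry date. Section 7.2.3 starts the study time frame in December 2014 at the earliest, so older records may not have been extracted.

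Both rules use only information from before the index date, so neither selects on follow-up. Report for each cohort how many patients classed as naïve by the 365-day rule had earlier ACEI or ARB records, separately for the two classes, and interpret the 365-day hazard ratio in that light. Keep the 365-day definition for the single-arm incidence rates.

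The cost is an added flag in the common program and a smaller cohort 2 in this analysis. Section 7.9 already warns that the naïve comparison may be underpowered, so the lost precision is real; that is why this is proposed alongside the 365-day analysis and not as its replacement.
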